8.1.2 Primary Safety Hypothesis

The primary safety endpoint is the rate of 12-month freedom from major adverse events. Major adverse events are defined as: clinical perforation, clinical migration, clinical fracture, embolization of the filter or filter fragments to the heart or lungs, IVC thrombotic occlusion, new symptomatic DVT while a filter is indwelling, access site complications with clinical sequelae, and procedure-/device-related death. The analysis requires that the performance goal of 80% be met for freedom from major adverse events at 12 months. The performance goal was derived based on what are considered clinically acceptable rates for each complication in the overall population.⁴⁸

The null (H_0) and alternative (H_A) hypotheses are expressed as follows:

$$H_0: S(t) \leq 80\%$$

$$H_a: S(t) > 80\%$$

where:

- t is time through 12 months
- $S(t)$ is the true rate of freedom from major adverse events at time t .

The hypothesis will be assessed using a Z-statistic. The Z-statistic is given by

$$Z = (\hat{S}(t) - 0.8)/SE$$

where:

- $\hat{S}(t)$ = Kaplan-Meier estimate of freedom from major adverse events ($S(t)$) at 12 months
- SE = Standard Error = $\sqrt{V(S(t))}$, where $\hat{V}(\hat{S}(t))$ is the estimate of the variance of the Kaplan-Meier estimate using the methods described by Peto et al.⁵⁰

The performance goal will be said to have been met provided the null hypothesis is rejected in favor of the alternative if $\hat{S}(t) - 0.8 > Z_{\alpha}SE$, for $\alpha = 0.025$. The hypothesis will be tested only for patients receiving Celect[®] filters.

8.2 General Statistical Analyses

Statistical analysis will be performed using SAS[®] for Windows[®] (release 9.3 or higher) or other widely accepted statistical software. Clinically-relevant baseline variables will be tabulated by each stratum. Continuous variables will be reported as means and standard deviations unless otherwise noted. Categorical variables will be reported as percent. Unadjusted 95% confidence intervals will be presented for the secondary endpoints, with a footnote specifying that they are unadjusted. Survival analysis techniques such as Kaplan-Meier or Cox Proportional Hazards will be incorporated if censoring of data occurs.

8.3 Sample Size

The study is designed to enroll 320 patients in the Celect[®] filter stratum (to evaluate the safety and effectiveness hypotheses) and up to 150 patients in the Günther Tulip[®] filter stratum at up to 40 sites globally. At least half of the study patients in the Celect[®] filter stratum will be enrolled at US sites.

For the primary effectiveness endpoint, based on what are considered clinically acceptable rates for technical placement success and new symptomatic PE in the overall

population, a performance goal of the rate of technical placement success and 12-month freedom from new symptomatic PE while a filter is indwelling was established to be 90%.⁴⁸ Additionally, based on the data from previous Cook sponsored studies (as summarized in Section 4.0), the rate of technical placement success and 12-month freedom from new symptomatic PE while a filter was indwelling was estimated to be 98.4% for the Celect[®] filter stratum. A sample size of 70 patients will be required to assess the primary effectiveness hypothesis for the Celect[®] filter stratum, with a one-sided exact binomial test, at a type I error rate of 0.025, and a power of 0.9. The calculation was performed with the SAS UnifyPow macro.

For the primary safety endpoint, based on what are considered clinically acceptable rates for each complication in the overall population, a performance goal of the rate of 12-month freedom from major adverse events was established to be 80%.⁴⁸ Based on the data from previous Cook-sponsored studies (as summarized in Section 4.0), the rate of 12-month freedom from major adverse events was estimated to be 92.2% for the Celect[®] filter stratum. A sample size of 88 patients will be required to assess the primary safety hypothesis for the Celect[®] filter stratum, with a one-sided exact binomial test, at a type I error rate of 0.025, and a power of 0.9. The calculation was performed with the SAS UnifyPow macro.

Based on sample size calculations, a minimum of 88 patients in the Celect[®] filter stratum will be required to evaluate the safety and effectiveness endpoints. Cook intends to enroll 320 patients in the Celect[®] filter stratum; this sample size allows for an attrition rate of 72% (i.e., 60% of filters to be retrieved prior to 12 months and an additional 12% of patients who may die, withdraw, or become lost to follow-up). The study may also enroll up to 150 patients in the Günther Tulip[®] filter stratum.

8.4 Missing Data

If the amount of missing data does not result in a reduction of analyzable patients to a number that is below that which is required for sufficient statistical power of the primary endpoints, case deletion will be the primary method to handle missing data.

However, if missing data results in a reduction of analyzable patients to a number that is lower than what is required for sufficient statistical power of the primary measures, then missing data will be addressed using multiple imputation with best available data, if

appropriate. This method will be used to predict missing endpoint and imaging data. Previous clinical trial experience suggests that some portion of the imaging data may not meet the criteria for accurate review by the core laboratory; however, it is recognized that the investigator uses this information to provide the best possible care for the patient. Therefore, it is reasonable to substitute any missing core laboratory measurements with the corresponding measurements made by the investigator or institutional staff.

Statistical imputation strategies originating from Schafer may also be used, supplemented with notes provided by Shafer.^{51,52} All missing endpoint and covariate data will be imputed with the values simulated from their respective empirical distributions. The computations (with no covariates) will be performed using five imputed datasets and PROC MI and PROC MIANALYZE in SAS version 9.3, or WinBUGS 1.4 or later. Unless evidence suggests otherwise, missing at random data will be assumed.

Additional analyses may also be performed to address missing data, including tipping point analysis.

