7.7 Post-Placement Follow-up

Follow-up windows are intended as guidelines only. They are not absolute and are not intended to limit data collection due to scheduling conflicts.

- *3 Months Post-Placement (90 ± 15 days):* Office visit including an assessment of the need for continued filtration, and an assessment of medications, hospitalizations, and medical conditions.
- *6 Months Post-Placement (180 ± 30 days):* Telephone contact by the clinical site to assess hospitalizations and medical conditions. Up to three attempts should be made to contact the patient.
- *12 Months Post-Placement (365 ± 30 days):* Office visit including an assessment of the need for continued filtration, and an assessment of medications, hospitalizations, and medical conditions. An abdominal CT with contrast to assess filter leg interaction with the IVC, a 2-view device X-ray to assess device integrity (the X-ray should be performed in AP and LAT views), and duplex ultrasound (IVC, bilateral pelvic veins, and bilateral lower extremity veins) to assess thrombus/DVT will be performed.
- *18 Months Post-Placement (540 ± 60 days):* Telephone contact by the clinical site to assess hospitalizations and medical conditions. Up to three attempts should be made to contact the patient.
- *2 Years Post-Placement (730 ± 60 days):* Office visit including an assessment of the need for continued filtration, and an assessment of medications, hospitalizations, and medical conditions. An abdominal CT with contrast to assess filter leg interaction with the IVC will be performed.

The need for continued filtration will be assessed based on each patient's overall medical condition. The decision to proceed to a retrieval attempt should also be based on factors such as the patient's ability and willingness to undergo the retrieval procedure and the physician's assessment of the risk/benefit ratio associated with the retrieval procedure.

If at any time during follow-up a patient presents with adverse clinical symptoms potentially related to his/her indwelling filter or the development of DVT/PE, appropriate assessments and treatment should be conducted according to the institution's standard of care. Clinical and imaging findings will be documented on the appropriate CRFs. For example:

- If the physician suspects a vena cava perforation, an abdominal CT with contrast will be performed to assess filter leg interaction with the IVC.

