APPENDIX C

Definitions

Access site complications with clinical sequelae - Arteriovenous fistula, hematoma, or bleeding requiring transfusion (≥ 2 units), hospitalization (either admission or extended stay), or further treatment.

Access site thrombus – Occlusive or nonocclusive thrombus developing at venotomy site after filter insertion or retrieval, documented by ultrasound or other imaging.

Adverse events – Definition may be found in applicable regulations.

Adverse device effects – Definition may be found in applicable regulations.

Clinical fracture – A loss of structural integrity (breakage or separation) of the filter identified by imaging and associated with clinical sequelae and/or requiring intervention.

Clinical migration – Caudal or cranial movement of a filter resulting in surgical or endovascular intervention.

Clinical perforation – Protrusion of filter legs through the wall of the IVC causing hemorrhage or hematoma or touching, impressing, or perforating another organ (e.g., liver, bowel, aorta, psoas muscle, vertebral body, lymph nodes). Acute perforation occurring during placement of the filter is considered a placement problem. Documented using CT.

Deep vein thrombosis (DVT) – Thrombus in the deep veins, usually of the lower extremities or pelvis. Documented by contrast venography, duplex ultrasound, CT, or magnetic resonance (MR) venography. The proximal extent of thrombus should be identified.

Device deficiencies – Definition may be found in applicable regulations.

Filter deformation – Insufficient opening of filter (i.e., filter legs do not adjust themselves to the size of the IVC), collapse of filter, uneven distribution of filter legs, bending of filter, or crossing or entangling of two or more filter legs.

Filter embolization – Post-placement movement of the filter or its components to a distant anatomic site completely out of the target zone (i.e., heart/lungs). Documented by imaging or autopsy.

Filter fracture – Any loss of structural integrity (breakage or separation) of the filter identified by imaging or autopsy. Documented by imaging or at autopsy.

Filter leg interaction with the IVC¹ –

- Grade 0: Normal; filter strut confined entirely within the IVC.
- Grade 1: Filter strut is immediately adjacent to the external aspect of the IVC wall (likely reflecting tenting of the IVC wall).

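### Case deletion does not suit the Kaplan-Meier safety test: the plan has no sound rule for a patient still in follow-up with no 12-month imaging

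*Combined protocol and SAP*

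**What the plan says.** - **Test (8.1.2).** "The analysis requires that the performance goal of 80% be met for freedom from major adverse events at 12 months". The statistic is built on the "Kaplan-Meier estimate of freedom from major adverse events" with a Peto-type variance. The section gives no censoring rule and does not require imaging before a patient counts as event-free.
- **MAEs that can be silent (Appendix C).** Clinical perforation is protrusion of filter legs "causing hemorrhage or hematoma or touching, impressing, or perforating another organ"; it needs no symptom and is documented by CT. IVC thrombotic occlusion counts whether or not it causes symptoms.
- **When they are looked for (Table 6.1 and 7.7).** "An abdominal CT with contrast to assess filter leg interaction with the IVC" is scheduled at 12 and 24 months and duplex ultrasound at 12 months. Before that, CT or duplex after placement is prompted by clinical suspicion.
- **Missing data (8.4).** While enough analyzable patients remain for power, "case deletion will be the primary method to handle missing data". Below that number, multiple imputation is used if appropriate, and it expressly covers endpoint and imaging data. Site readings may replace missing core laboratory readings. Tipping-point analysis is optional.

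**The concern.** Consider a patient with the filter in place, no MAE so far, still in follow-up, and no 12-month imaging. A site reading cannot stand in for a scan that was never done. The stated rule deletes this patient. A patient who had an MAE in month 4 has a known outcome and stays. Deletion therefore depends on outcome: it removes event-free follow-up from every earlier risk set but removes no events.

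The alternative that arises by default is no better. Patients with the filter in place are followed to 24 months, so an ordinary time-to-event dataset carries an unscanned patient past day 365 as event-free unless a rule prevents it. That biases the rate upward.

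The plan expects only about 90 Celect patients at the 12-month scan. One dataset can thus give different answers according to a choice that could be made after the data are seen, in a single-arm test against a fixed goal.

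**Working it through.** **The plan's own figure.** 8.3 states: "A sample size of 88 patients will be required to assess the primary safety hypothesis", "with a one-sided exact binomial test, at a type I error rate of 0.025, and a power of 0.9", for 80% against an expected 92.2%. With n = 88 the critical value is 78 event-free patients. The exact type I error is 0.0238 and the power 0.919. No smaller n from 70 upward reaches 0.90, so 88 reproduces. Enrolment of 320 with 72% attrition (60% retrieved, 12% other) leaves 320 × 0.28 = 89.6.

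**Assumptions, not in the documents.** True freedom is 80%. Attrition is uniform over the year. Overt MAEs (12-month probability p) have a constant hazard. Silent MAEs are found only at the scan (probability q among those who reach it MAE-free). A share m = 20% of scans is missing at random.

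| Case | p | q | True rate (1−p)(1−q) | Scan-only share of MAEs, (1−p)q / [1−(1−p)(1−q)] |
|---|---|---|---|---|
| A | 0.08 | 0.13 | 0.800 | 0.60 |
| B | 0.04 | 0.167 | 0.800 | 0.80 |
| C | 0.15 | 0.0588 | 0.800 | 0.25 |

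**Unscanned carried as event-free.** Expected estimate = (1−p)[1−q(1−m)].
- A: 0.92 × (1 − 0.104) = 0.824
- B: 0.96 × (1 − 0.1336) = 0.832
- C: 0.85 × (1 − 0.0471) = 0.810

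**Unscanned deleted.** The number at risk at time t (in years) is n(t) = 320(1−0.72t)(1−p)^t. Deletion removes D = 0.2 × 89.6 × (1−p) patients from every risk set and no events. With λ = −ln(1−p), the overt part becomes exp{−∫λ n(t)/[n(t)−D] dt} over 0 to 1, which is then multiplied by (1−q).
- A: D = 16.5; 0.912 × 0.87 = 0.793
- B: D = 17.2; 0.956 × 0.833 = 0.796
- C: D = 15.2; 0.836 × 0.941 = 0.787

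**Unscanned censored just before the scan.** The silent probability is estimated among those scanned and the overt part is untouched, so the expected estimate is 0.80 in all three cases.

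**False-pass rate by simulation.** The test is Z > 1.96, with the Peto standard error taken as S√[(1−S)/n], n being the number at risk at 12 months. Ranges cover repeat runs and, for A and B, taking n just before or just after the scan.

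| Case | All scanned | Event-free | Deleted | Censored |
|---|---|---|---|---|
| A | 3-4% | 10-11.5% | 2-2.5% | 3-3.5% |
| B | 4-4.5% | 16-18% | 3-4% | 4-4.5% |
| C | 1.5-1.8% | 2.6-2.9% | 0.5% | 1.1% |

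With a Greenwood standard error, case C under the event-free handling rises from 4-5% to about 7.8%. If no MAEs are scan-only, the event-free handling has no effect.

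**Imputation.** With the scan result imputed among patients MAE-free up to the scan (five imputations, Greenwood), the mean estimate is 0.798-0.800 and the false-pass rate 4.4-5.3% for scan-only shares of 25-100%.

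**Its trigger.** If analyzable means patients with a 12-month result, on the plan's own count, 89.6 − 2 = 87.6 is already below 88, and 20% missing leaves about 72. If it means everyone in the curve, the trigger is never reached, because no missing scan removes anyone from the 320.

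**The case against.** The strongest reply is that 8.4 has a third branch. On the count of patients with a 12-month result, two missing scans move the analysis to multiple imputation, which is nearly unbiased under missing at random. That stands, but only on one reading of an undefined term. The branch is also conditional on being judged appropriate and is specified without covariates. If the binary 12-month endpoint is imputed that way, the deletion estimate comes back.

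A reader might infer that the plan counts unscanned patients as event-free, or that its false-pass rate is 11-17%. The documents do not support this. No section states that handling, and 8.4 treats absent imaging as missing data, which points away from it. The figure also needs most MAEs to be scan-only. The documents give no such share. Table 4.2 lists acceptable rates below 2% for perforation and below 5% for caval thrombosis or occlusion, and Table 4.3 reports 0% (perforation with clinical sequelae) and 0.14%. Those definitions may be narrower than the CT-based one here, but they are no evidence for 13-17% silent events.

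Nor does the quoted rule raise false passes when scans are missing at random: deletion is then conservative.

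Venacavagrams before and after retrieval also examine the IVC, and venography can document occlusion. They cover retrieved filters, not a filter still in place at 12 months.

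At the expected 92.2% the choice matters little. With half of MAEs scan-only and 20% of scans missing, the pass probability (Greenwood) is 98% with full scans, above 99% under the event-free handling and 95% with imputation.

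**Conclusion.** The point holds as a fault in a stated rule plus an open definition. Case deletion makes the Kaplan-Meier estimate depend on outcome and biases it low, by roughly 0.3 to 1.4 percentage points at 20% missing at random. The plan does not exclude the opposite handling, which biases the estimate upward by 1.0 to 3.2 points in the three cases. The change in false-pass rate runs from slight (about 1.5% to 2.6%) to material (about 4% to 11-17%), depending on a scan-only share that has to be assumed. Whether imputation applies turns on a word the plan does not define.

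The direction of the deletion bias relies on random missingness. If patients with a silent event are 1.5 times as likely to go unscanned, and half to three quarters of MAEs are scan-only, deletion gives 80.2-81.1% and censoring 81.2-81.6% for a true 80%, with Greenwood false-pass rates of 5.5-7.9% and 8.7-9.8%. Censoring is the better primary rule under the plan's missing-at-random assumption, but it does not protect against that pattern. This should be settled before analysis; it does not call the design into question.

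**What to change.** In 8.1.2 and 8.4:

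1. For the safety endpoint, replace case deletion by censoring just before the 12-month imaging. Apply it to any patient with the filter in place, no prior MAE, and no imaging adequate to assess organ contact and IVC occlusion. An adequate contrast CT suffices without duplex, since CT can document occlusion and DVT counts only if symptomatic. A late scan is not a missing scan, because 7.7 treats visit windows as guidelines.
2. Define analyzable for the Kaplan-Meier analysis. If imputation is kept, state that it models the missing scan result among patients MAE-free up to the scan.
3. Make the tipping-point analysis mandatory. Counting every unscanned patient as an MAE should be only its extreme end: with 20% unscanned, that alone caps the estimate at 0.80 and forces failure even with no true events.
4. Report the number of unscanned patients.

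The cost is SAP wording and a small extra analysis. Slightly fewer patients are at risk at 12 months, so the interval is slightly wider. Censoring is unbiased only if scans are missing at random, which is why item 3 should not be optional.

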3.2 Indication for Use

The Günther Tulip[®] filter and the Cook Celect[®] filters are intended for the prevention of recurrent PE via placement in the vena cava in the following situations:

- Pulmonary thromboembolism when anticoagulant therapy is contraindicated;
- Failure of anticoagulant therapy in thromboembolic diseases;
- Emergency treatment following massive PE where anticipated benefits of conventional therapy are reduced; and
- Chronic, recurrent PE where anticoagulant therapy has failed or is contraindicated.

In addition to the specific labeled indications, it is well-documented in clinical practice guidelines that IVC filters have additional clinical indications, and are frequently placed in patients with the following: severe trauma, closed head trauma, spinal cord injury,

multiple long-bone or pelvic fractures, or other conditions putting them at high risk for PE (e.g., prolonged immobilization, pre-/post-operatively).⁵⁻⁸ Outcomes from use in these broad patient populations have been widely reported in the literature^{1-3,9-22}, including those based on results of previous studies for the Cook IVC filters.¹⁻³ Based on available data, patient outcome is not specifically related to indication for filter placement, but may be related to each patient's overall medical condition, including the patient's state of hypercoagulability, body mass index, use of anticoagulation, comorbid conditions, etc. Moreover, Cook has conducted three previous studies of the performance of its permanent and retrievable IVC filters in a broad patient population,¹⁻³ and the results (or interim results) of these studies are included in product labeling. Furthermore, these broad patient populations were included in the indications for use that were approved in the PMA for the Cook Bird's Nest[®] Vena Cava Filter (P850049).

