In addition to these data, a wide body of clinical literature supports filter efficacy in a broad range of patient populations. These include data from primarily single and multicenter studies of individual filter types, and some randomized studies comparing outcomes with different filter types. Based on Cook's ongoing analysis of the published literature, IVC filter use in a broad patient population is associated with a low PE rate (an average of 1.7%).^{2,3,11-13,19,21,23-41} This rate is much lower than that observed in the PREPIC study; moreover, this rate is lower than the expected PE rate in specific patient populations (for example, a literature review suggests that the PE rate in trauma patients without an IVC filter is approximately 4.9%). In general, the data are supportive of the use of filters to prevent PE, though there are important covariates that may impact patient outcomes (e.g., history of VTE, anticoagulation scheme).

The benefit of filter placement in specific patient populations has also been discussed in the literature, including:

- A recent systematic review of 24 studies describing filter placement in trauma patients, in which the authors concluded that (for the trauma population) filter-related complications are infrequent (and those that do occur tend not to be clinically-significant) and that filter placement does reduce the incidence of PE and PE-related mortality.⁴²
- A recent assessment of the impact of IVC filters on in-hospital fatality due to PE based on the Nationwide Inpatient Sample using ICD-9-CM codes to identify patients with PE. Results of the analysis suggested that IVC filter placement resulted in significantly fewer in-hospital fatalities in: 1) unstable patients with PE (regardless of the use of thrombolytic therapy; 33% vs. 51% in patients without thrombolytic therapy and 7.6% vs. 18% in patients with thrombolytic therapy; $p<0.0001$); and 2) stable patients receiving thrombolytic therapy (6.4% vs. 15%; $p<0.0001$). The incidence of in-hospital fatality in stable patients not receiving thrombolytic therapy was also significantly reduced (7.2% vs. 7.9%; $p<0.0001$), though this reduction was not as clinically-meaningful as for the other populations.⁴³

Therefore, the clinical body of evidence supports filter placement for the prevention of PE in a broad range of patients.

Filter Safety

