8.5 Site-level Poolability

At the final analysis, poolability of data from multiple sites will be verified by examining the primary safety and effectiveness endpoints using logistic regression models. Site-level poolability will be considered appropriate provided that these measures are similar among sites.

It is expected that some sites may have too few patients to provide reasonable site-level estimates of the primary measures. Each investigative site will be allowed to enroll no more than 20% of the patients in each stratum to ensure the overall results are not biased by the results from a single site. Pooling of this information will be explored based on hospital size (large versus small, determined based on number of beds and annual number of discharges), site enrollment (large versus small), type of hospital (community versus teaching), and other group-wise strategies.

It is recognized that patient baseline characteristics may differ among sites, with some sites routinely treating specific patient types (e.g., trauma patients). It is anticipated that the primary endpoint measures may be related to covariates that reflect this. Thus, observed site-specific differences among the primary endpoints will be checked for

confounding with other measured covariates (e.g., age, sex). This can be accomplished using logistic regression models that include site and other measured covariates as independent variables.

Should one or more sites be found to differ significantly from the rest, then logistic regression analysis will be performed with an intercept term and a covariate to distinguish between the unusual site(s) and those sites that are considered poolable. Analysis on the primary endpoints will be performed by constructing 95% confidence interval on odds ratio for the intercept term.

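### The low-power fallback in Section 8.4, read as covariate-free imputation in five datasets, adds no information, cannot restore power, and has no stated pooling rule

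*Combined protocol and SAP*

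**What the plan says.** Section 8.4 (Missing Data) keeps case deletion as the primary method while enough patients remain analysable. Below the number needed for power, "missing data will be addressed using multiple imputation with best available data", if appropriate. The values come from marginal distributions: "All missing endpoint and covariate data will be imputed with the values simulated from their respective empirical distributions". The next sentence fixes the scale of the work: "The computations (with no covariates) will be performed using five imputed datasets", run in PROC MI and PROC MIANALYZE or in WinBUGS. The assumed mechanism is: "Unless evidence suggests otherwise, missing at random data will be assumed". Sensitivity work is optional: "Additional analyses may also be performed to address missing data, including tipping point analysis".

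Elsewhere the document expects outcomes to depend on patient characteristics. Section 3.2 links outcome to the patient's "state of hypercoagulability, body mass index, use of anticoagulation, comorbid conditions, etc". Section 4.0 says "there are important covariates that may impact patient outcomes (e.g., history of VTE, anticoagulation scheme". Section 8.5 says of differing patient types across sites: "It is anticipated that the primary endpoint measures may be related to covariates that reflect this".

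Section 8.4 does not say how the exact binomial test (8.1.1) or the Kaplan-Meier Z-test (8.1.2) is to be carried out on imputed data, whether model parameters are drawn, or whether patients whose filters were retrieved are to be imputed.

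**The concern.** The switch is made because power is short, so the replacement method ought to recover information. Imputing an endpoint from its own marginal distribution cannot do that. The draws repeat what the observed patients already show and add simulation noise. They are unbiased only if data are missing completely at random, as with case deletion, and the stated missing-at-random assumption is never used.

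The wording is ambiguous. The phrase about covariates could describe the analysis model, and the preceding sentence speaks of imputing covariates too. A primary-analysis fallback should not rest on that ambiguity.

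What is at stake is the effectiveness claim for the Celect stratum. Depending on choices the plan leaves open, a filter performing as planned could miss its goal because of the fallback, or the false-positive rate could exceed 0.025.

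**Working it through.** **Inputs.** Goal 90%, one-sided exact binomial at 0.025 (8.1.1). Planned rate 98.4%, effectiveness n = 70, safety n = 88, enrolment 320, attrition 60% retrieval plus 12% other (8.3). Five datasets (8.4).

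**The plan's own figures.** n = 70 passes at 68 or more successes: level 0.0242, power 0.898, which agrees with the stated 0.9 to rounding. Safety n = 88 (80% against 92.2%) passes at 78 or more: level 0.0238, power 0.919. Both reproduce.

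**Scenario.** 87 observed, one below the overall minimum of 88. The exact test passes at 84 or more: level 0.0211, power 0.9486. The number after imputation is an assumption:
- N = 128 excludes retrieved patients: 320 − 0.60 × 320 = 128, so 41 are imputed, close to the planned 12% loss (38).
- N = 320 imputes retrieved patients as well, so 233 are imputed.

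**Information.** With draws at the observed rate, the variance of the pooled estimate is p(1−p)[1/n + (N−n)/(mN²)], which is never below the complete-case p(1−p)/n. At p = 0.90, n = 87, N = 128, m = 5:
- Imputed: 0.09 × (0.01149 + 0.00050) = 0.00108, SD 0.0329.
- Complete case: 0.09/87 = 0.00103, SD 0.0322.

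Drawing the parameter as well adds a little more (simulated SD 0.033 at N = 128 and 0.034 at N = 320). No precision is gained.

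**Level and power.** Simulation: x ~ Binomial(87, p), with p = 0.90 for level and 0.984 for power. Proper draws: θ ~ Beta(x + 0.5, 87 − x + 0.5), then a binomial draw for the remainder. Pooling: r = (1 + 1/m)B/W, df = (m − 1)(1 + 1/r)², t reference, at least 60,000 trials. Wilson-type statistic: (q̄ − 0.9)/√[(0.09/N)(1 + r)]. The logit carries a 0.5 correction. The score scale fixes the within-variance at 0.09/N.

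N = 128, m = 5:

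| Method | Level | Power |
|---|---|---|
| Exact test on the 87 | 0.021 | 94.9% |
| Logit | 0.011 | 68% |
| Wilson-type | 0.016 | 75% |
| Score | 0.026–0.027 | 92% |
| Proportion | 0.058–0.059 | 97% |

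The excess on the proportion scale is a Wald effect: complete-case Wald error is already 5.7%.

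**Number of datasets.** At m = 50 and N = 128, power is 85% (logit) and 88% (Wilson-type). For logit, 17 of the 27 points lost come back (85 − 68, out of 95 − 68). For Wilson-type, 13 of 20 come back. Complete-case logit power is 83.7%, so the remaining logit shortfall belongs to that test.

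**Literal draws at the observed rate.** The ratio of stated to true standard error is √{[1/N + 1.2(N−n)/N²] / [1/n + (N−n)/(5N²)]}.
- N = 320: √(0.005855/0.011949) = 0.70. Simulated error is 6.7% (logit), 7.4% (Wilson-type), 10.0% (score) and 12.4% (proportion).
- N = 128: √(0.010815/0.011995) = 0.95. Logit (1.6%) and Wilson-type (2.3%) hold the level, with power 85% and 90%.

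**Where the power loss does not occur.** At 69 observed the exact test needs 68 successes: level 0.0060, power 0.697. With 10 missing (N = 79), score pooling has level 0.019 and power 0.83. It uses alpha that the discrete test leaves spare. With N = 128 the score scale no longer holds the level (0.033), and Wilson-type power is 55%.

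**Chance of the switch.** Expected analysable patients at 28% retention: 320 × 0.28 = 89.6. From Binomial(320, retention), P(87 or fewer) is 0.400 at 28%, 0.150 at 30%, 0.036 at 32% and 0.002 at 35%. P(69 or fewer), below effectiveness's own 70, is 0.005 at 28%.

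**The case against.** The strongest reply is that the power comparison is not general, and this stands. A reader might infer that any pooling that keeps 0.025 has less power than the exact test. The 69-observed example refutes that, although the gain there is not recovered information. Completing 69 to 79 would also imply 241 of 320 retrieved, about 75% against the planned 60%.

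A reader might also take 40% as the chance that the effectiveness analysis is affected. That holds only if the safety-driven minimum of 88 governs both endpoints. The plan does not say so, and at 87 patients effectiveness is still well powered.

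A third tempting inference is a false-positive rate near 12%. It needs literal draws, proportion-scale pooling, and imputation of retrieved patients. Section 8.3 calls retrievals attrition, but 8.4 never calls them missing data, and 6.3.1 limits the endpoint to the time a filter is indwelling.

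A material missing-at-random bias is not established either. At a mean of 98.4%, two equal groups differ by at most 3.2 points. Assumed retention ratios R of 1.5 to 2.0 then give at most 3.2 × [R/(R+1) − 0.5] = 0.3 to 0.5 points, against a planned margin of 8.4.

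Section 8.4 also allows site readings to replace missing core-laboratory readings, which adds real data and is not criticised here. Finally, omitting covariates has a practical defence: 87 × 0.016 is about 1.4 expected failures, too few for a rich model.

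What survives is that the one imputation computation specified cannot do what triggers it, and the choices that decide its level and power are not stated.

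**Conclusion.** The point holds in this limited form. If the covariate phrase governs the imputation model, the fallback adds no information and cannot restore power. In the main scenario (87 observed, 128 after imputation, proper draws, five datasets), the two scales that hold the level cost about 20 to 27 points of effectiveness power. The two that largely keep power exceed the level, one slightly and one clearly. Most of the logit and Wilson-type loss is due to five datasets. Error of about 7% to 12% arises with literal draws when retrieved patients are also imputed.

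The chance that this matters runs from about 40% to near nil, depending on which minimum governs and whether retrieved patients count as having outcomes. The figures cover the binary effectiveness endpoint only; the Kaplan-Meier safety test was not modelled. The plan should be changed, with medium confidence in the practical consequence.

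**What to change.** - Remove the switch based on analysable numbers. Keep the exact binomial test (8.1.1) and the Kaplan-Meier Z-test (8.1.2) as primary at any number.
- State that patients with retrieved filters are handled by the endpoint definition and are not imputed.
- Use multiple imputation only as a sensitivity analysis, with proper draws, a stated pooling scale and many more than five datasets (for example 50). Because few failures are expected, limit it to one or two prespecified covariates or a penalised model.
- Make the tipping-point analysis planned instead of optional.

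The cost is SAP wording and minor programming, with no new data. The drawback is that a shortfall in analysable patients would be reported openly as reduced power.
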